PAP was first identified in 1938 and was initially used as a serum marker for the detection of prostate cancer [15, 24]. PAP expression in normal and malignant prostate cells is well-documented, and is still used in immunohistochemical staining to establish a prostate origin of metastatic carcinoma [25]. The ubiquitous expression of PAP in prostate tissue makes it an appealing antigen as a potential “universal” target for immune-directed therapies of prostate cancer, unlike specific oncogenes that may or may not be expressed by a particular tumor. Moreover, it has been demonstrated that some patients with prostate cancer have preexisting antibody and T-cell responses to PAP, suggesting that tolerance to this “self” protein can be circumvented *in vivo* [26, 27]. In particular, the demonstration of Th1-like immune responses specific for PAP suggest that an immune environment permissive of an anti-tumor response can exist in patients even without immunization [28]. Moreover, we have previously demonstrated that CD8+ T cells specific for PAP, with cytolytic activity for prostate cancer cells, can exist in patients with prostate cancer, and can be augmented with vaccination [23, 28].

B. Sipuleucel-T: The first anti-tumor vaccine FDA approved for the treatment of cancer

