The current protocol will examine the use of a plasmid DNA vaccine encoding PAP to induce and/or augment T-cell immune responses to PAP in patients with castrate-resistant, metastatic prostate cancer following treatment with sipuleucel-T. Based on published results from trials conducted with sipuleucel-T, PA2024 and PAP antibody and proliferative T cell responses have been observed, suggesting a possible CD4+ T-cell-biased immune response. In 25 individuals who have received multiple immunizations with the pTVG-HP DNA vaccine, no PAP-specific antibody responses have been observed, and multiple individuals have had detectable Th1-biased PAP-specific CD4+ and CD8+ responses. These results suggest that different types of immune responses to the same antigen might be elicited depending on the type of immunization, and hence a combination able to elicit a broad immune response might have greater anti-tumor effect. Given that a Th1/CD8+/CTL response would be predicted to be the most effective immune response elicited capable of lysing PAP-expressing prostate cancer cells, the identification of these specific subsets will be the primary endpoint of this pilot trial. The trial will be conducted in patients with minimally symptomatic, castrate-resistant, metastatic prostate cancer, as this is the approved indication for treatment with sipuleucel-T. In addition, given previous observations from clinical trials using sipuleucel-T, and multiple other anti-tumor vaccine trials, suggesting that clinical effects (unlike with standard cytotoxic therapies) might occur months after treatment

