3. To evaluate effects of treatment on changes in serum PSA level and changes in PSA doubling time

C. Laboratory and Exploratory Objectives:

1. To determine overall survival
2. To evaluate effects of treatment on number of circulating tumor cells as determined by PSA ELISPOT
3. To evaluate PAP-specific antibody and T-cell immune responses following treatment with sipuleucel-T and DNA vaccine
4. To determine whether PAP-specific immune response is associated with prolonged (1 year) radiographic progression-free survival
5. To determine whether baseline immune responses (Th1 type or regulatory type) predict for immune responses elicited/augmented following treatment with sipuleucel-T +/- DNA vaccine
6. To determine whether treatment elicits immunologic antigen spread to other prostate associated antigens

4. Product Information

A. Sipuleucel-T

PA2024

PA2024 is a recombinant fusion protein consisting of human PAP and GM-CSF. GM-CSF acts as a growth factor and differentiation factor for antigen-presenting cells, including dendritic cells; the purpose of the fusion protein is to direct the PAP antigen to antigen-presenting cells *in vitro*, and promote antigen uptake and processing of the PAP antigen.

Preparation of sipuleucel-T

Patients will undergo a standard 1.5-2.0 blood volume leukapheresis to harvest peripheral blood mononuclear cells. This procedure will be performed either at the UWHC Infusion Center or a contract provider authorized by Dendreon Corporation. Immediately after collection, the product

will be transported by air carrier to a Dendreon-approved national cell processing facility. There, the cell product will be enriched for antigen-presenting cells by proprietary buoyant density centrifugation techniques, and cultured *in vitro* in the presence of PA2024 for 36-44 hours. After the culture period, the cells will be washed and resuspended in Lactated Ringer's Injection, USP. The sipuleucel-T cell product will then be shipped back to the UWHC for infusion at the UWHC Infusion Center. During shipment, sterility testing and cell count data are gathered for final product release for re-infusion. These procedures will all be performed as part of the standard-of-care for the FDA-approved sipuleucel-T product and re-infusion.

B. Plasmid DNA vaccine

pTVG-HP (pTVG4 vector containing cDNA for human PAP)

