The presence of a coexisting humoral immune response to PAP will be evaluated by ELISA using an indirect method similar to that described previously [26]. Specifically, Immulon-4 ELISA plates (Dynex Technologies Inc.) will be coated with $2 \mu\text{g/ml}$ purified PAP protein (Research Diagnostics, Inc.) in $0.1 \text{ M NaHCO}_3/\text{Na}_2\text{CO}_3$ buffer (pH 9.6) overnight at 4°C . After blocking with PBS/1% BSA for 1 hour at room temperature, wells will be washed with PBS + 0.05% Tween-20 (PBS-Tween) and then incubated for 1 hour with human sera diluted 1:25, 1:50, 1:100 and 1:200. After washing, plates will then be sequentially incubated with a peroxidase-conjugated anti-human IgG detection antibody (Amersham), followed by peroxidase enzyme TMB substrate (Kierkegaard and Perry Laboratories). The color reaction will be stopped with $1\text{N H}_2\text{SO}_4$ and the optical density measured at 450 nm. Antibody titers for PAP-specific IgG antibodies will be determined as previously described [26].

REPORTING AND RESPONSE DEFINITION: These are not strictly quantitative assays. IgG response will be reported graphically demonstrating sera dilution curves, and by titer – defined as the highest sera dilution at which IgG responses are detectable above the mean + 3 standard deviations of the negative control. A positive IgG response resulting from immunization will be defined as an antigen-specific (anti-PAP) IgG titer at least 4-fold higher than the baseline titer detectable at the 6-month post-treatment time point (or other post-treatment time point evaluated).

A.4. Assessment of antigen-specific regulatory immune responses

Trans-vivo delayed-type hypersensitivity (tvDTH) evaluation: $7.5\text{-}10 \times 10^6$ PBMC obtained from patients prior to and after immunization will be co-injected into the footpads of 6-to-8-week old SCID mice with $1 \mu\text{g}$ of PAP protein (Fitzgerald Industries, Acton, MA), or tetanus toxoid (TT/D; Aventis Pasteur, Bridgewater, NJ) as a recall antigen, versus phosphate-buffered saline (PBS) alone as a negative control. Antigen-driven swelling will be determined as previously described [52]. DTH reactivity after 24 hours will be shown as the change in footpad thickness in multiples of 10^{-4} inches, measured using a dial thickness gauge (Mitutoyo, Japan), and net

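### The 4-fold titer rule for a PAP IgG response in 10.A.3 cannot be met from a baseline of 1:100 or 1:200, because sera are tested only to 1:200, and no value is set for sera negative at 1:25

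*Combined protocol and SAP*

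**What the plan says.** Section 10.A.3 describes an indirect ELISA for IgG against PAP in which plates are "incubated for 1 hour with human sera diluted 1:25, 1:50, 1:100 and 1:200". The titer is "defined as the highest sera dilution at which IgG responses are detectable above the mean + 3 standard deviations of the negative control". A positive response to immunization is an anti-PAP "IgG titer at least 4-fold higher than the baseline titer detectable at the 6-month post-treatment time point", and the same rule applies to any other post-treatment time point that is evaluated.

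The section does not list a dilution beyond 1:200, does not say what to do with a serum still positive at 1:200, and does not assign a value to a serum negative at 1:25. For titer determination it otherwise points to cited reference 26. It also qualifies the assay: "These are not strictly quantitative assays. IgG response will be reported graphically demonstrating sera dilution curves, and by titer".

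The antibody result serves laboratory and exploratory objective 3 in Section 3.C: "To evaluate PAP-specific antibody and T-cell immune responses following treatment with sipuleucel-T and DNA vaccine". Section 12.G.5.2 plans a table of these responses and nothing more. On background, Section 2.A notes that "some patients with prostate cancer have preexisting antibody and T-cell responses to PAP". Section 2.E says that with sipuleucel-T, "PA2024 and PAP antibody and proliferative T cell responses have been observed".

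**The concern.** The responder definition and the dilution series do not fit each other. Under the titer definition the result can only be one of the tested dilutions, so 1:200 is a hard ceiling. A 4-fold rise is two doubling steps, and the two highest baseline results leave fewer than two steps above them. A patient who enters with one of those titers is classified as a non-responder by construction, even if antibody rises many-fold.

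At the bottom of the range the difficulty is different. Without a value for a serum negative at 1:25, the fold change has no denominator, and the analyst must choose one.

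At stake is the tabulated proportion of antibody responders in each arm. It can be too low where patients bring pre-existing antibody, and it can move with a coding choice that the plan leaves open.

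**Working it through.** **Inputs, all from Section 10.A.3.** Attainable titers (as reciprocals): 25, 50, 100, 200. Response rule: post-treatment titer ≥ 4 × baseline titer. The plan states no figure of its own to reproduce.

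**Step 1: detectable baselines.** For baseline b, the required titer is 4 × b and the largest fold that can be recorded is 200 / b.

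| Baseline | Required (4 × b) | Tested dilutions that qualify | Largest recordable fold (200 / b) |
|---|---|---|---|
| 1:25 | 1:100 | 1:100, 1:200 | 8 |
| 1:50 | 1:200 | 1:200 | 4 |
| 1:100 | 1:400 | none | 2 |
| 1:200 | 1:800 | none | 1 |

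The rule is attainable from two of the four detectable baselines and impossible from the other two.

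**Step 2: baseline negative at 1:25.** No value is given, so assume one and take the lowest tested dilution at or above 4 × that value.

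| Assumed reciprocal for a negative serum | 4 × value | Lowest qualifying titer |
|---|---|---|
| 1 (any detectable titer counts) | 4 | 1:25 |
| 12.5 (one step below the series) | 50 | 1:50 |
| 25 (lowest dilution tested) | 100 | 1:100 |

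The cutoff therefore varies over three of the four dilutions.

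**Step 3: what one patient is worth.** Section 12.F assumes 14 evaluable patients per arm. If the antibody table uses that denominator, each patient misclassified in either direction moves an arm's rate by 1 / 14 = 7.1 percentage points.

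**Step 4: effect of a longer series.** With 1:400 and 1:800 added, a baseline of 1:100 can reach 1:400 or 1:800, and a baseline of 1:200 can reach 1:800. A baseline now recorded as 1:200 may prove higher on the longer series. A baseline of 1:400 would need 4 × 400 = 1:1600, and a baseline of 1:800 would need 4 × 800 = 1:3200. Hence 1:800 is a minimum, not a guarantee.

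**The case against.** The case for leaving the section alone has several parts.

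- **The endpoint is exploratory and only tabulated.** This stands. The primary endpoint in Section 12.C.1 uses three T-cell tests, and the sample size in 12.F rests on that response. Antibody enters neither.
- **The assay is declared not strictly quantitative, and dilution curves are shown as well.** This stands in part. Optical densities along the curve could show a shift in a serum whose titer is capped, unless the signal is saturated throughout. But the responder label is set by titer, and a semi-quantitative assay still needs categories that can be reached.
- **Reference 26 may hold a convention.** It is not available here, and it might cover the coding of negative sera. It is a weaker answer for the ceiling, since 10.A.3 sets out its own series.
- **The loss is recoverable.** True: sera are stored in aliquots (10.A) and kept indefinitely (16.C), so further dilutions can be run later. That makes the repair cheap, but it does not make the written rule work.

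A reader might also infer that high titers are to be expected, that both arms will pile up at 1:200, and that a difference between arms will be hidden. The documents do not support this. Section 2.A says only that some patients have PAP antibody, and Section 2.E says only that antibody responses have been seen with sipuleucel-T. Neither gives a titer or a frequency. Section 2.E also reports no PAP antibody response in 25 people given repeated pTVG-HP, which is the component that differs between the arms. And 12.G.5.2 plans no test of antibody response between arms.

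**Conclusion.** The defect is real and minor. As written, a baseline titer of 1:100 or 1:200 makes an antibody response impossible, and a baseline negative at 1:25 leaves the threshold undefined between 1:25 and 1:100. The first is a stated rule that misclassifies any patient whose true titer rises 4-fold from such a baseline. The second is a missing convention.

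The ceiling can only lower the tabulated response rate. By how much cannot be computed, because the number of patients with a baseline of 1:100 or above is not given; if there are none, the ceiling does no harm. The figure of 7.1 points per patient assumes 14 evaluable patients in the arm. The conclusion also assumes that the four listed dilutions are the whole series and that reference 26 does not extend them.

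**What to change.** In 10.A.3, extend the two-fold series to at least 1:800. If that is not done for every serum, do it at minimum for both the baseline and the post-treatment sera of any patient positive at 1:100 or 1:200 at baseline. Where a baseline serum is still positive at 1:400 or beyond, continue that patient's sera two doubling steps past the baseline titer.

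Add one sentence, before analysis, that assigns a single value to titers below 1:25. One example is 1:12.5, under which response requires 1:50 or more. The choice of value matters less than fixing it in advance.

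The cost is a few extra ELISA wells per serum, run on stored aliquots. No further blood or visits are needed, and the primary analysis does not change.

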1. To evaluate whether immunization with a DNA vaccine encoding prostatic acid phosphatase (PAP, pTVG-HP) can augment PAP-specific effector and memory T cells following treatment with sipuleucel-T.

[figure not shown]
Secondary Objectives:

1. To determine 12-month radiographic progression-free survival
2. To determine median time-to-radiographic progression as a function of baseline time point (pretreatment or 3-months post treatment)
3. To evaluate effects of treatment on changes in serum PSA level and changes in PSA doubling time

Laboratory and Exploratory Objectives:

1. To determine overall survival
2. To evaluate effects of treatment on number of circulating tumor cells as determined by PSA ELISPOT
3. To evaluate PAP-specific antibody and T-cell immune responses following treatment with sipuleucel-T and DNA vaccine
4. To determine whether PAP-specific immune response is associated with prolonged (1 year) radiographic progression-free survival
5. To determine whether baseline immune responses (Th1 type or regulatory type) predict for immune responses elicited/augmented following treatment with sipuleucel-T +/- DNA vaccine
6. To determine whether treatment elicits immunologic antigen spread to other prostate associated antigens

Study Scheme:

Study Calendar:

Vaccine / Treatment Visit:	Pre-Screen (within 4 weeks of Screen)	Screen/Randomization (within 2 weeks of day 1)	Day 1 – sipuleucel-T collection #1	Day 4 – sipuleucel-T infusion #1	Day 15 – sipuleucel-T collection #2	Day 18 – sipuleucel-T infusion #2	Day 29 – sipuleucel-T collection #3	Day 32 – sipuleucel-T infusion #3	Day 43 – sipuleucel-T follow-up / DNA imm #1 ^a	Day 57 – DNA imm #2 ^a	Day 71 – DNA imm #3 ^a	3-Month Followup (Day 85) – DNA imm #4 ^a	6-Month Follow up (Week 24) – DNA imm #5 ^a	9-Month Follow-up (Week 36) – DNA imm #6 ^a	12-Month (Week 48) Follow-up and/or End of study visit
History & Physical Exam															
History	X														
Consent	X														
Physical Exam, ECOG PS		X			X		X		X			X	X	X	X
Vital signs		X		X	X	X	X	X							
Toxicity assessment ^b		X			X		X		X			X	X	X	X
Injection site inspection									X	X	X	X	X	X	X
Lab Tests															
CBC with differential and platelets ^c		X			X		X		X			X	X	X	X
Creatinine, alk phos, SGOT, total bilirubin, amylase, LDH		X							X			X	X	X	X
Serology for HIV Ab/Ag combo, Hepatitis B Surface Ag, Hepatitis C AB		X													
Serum testosterone, ALT		X													
PSA ^d and PAP		X							X			X	X	X	X
Procedures															

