 pTVG-HP (100 μ g) with rhGM-CSF (208 μ g) administered intradermally (i.d.) biweekly 4 times, then every 3 months to complete a 1-year treatment period (i.e. weeks 6 (day 43), 8 (day 57), 10 (day 71), 12 (month 3), then months 6 and 9)

A. **Study Arm Assignment and Toxicity Assessment**

Patients with asymptomatic-to-minimally-symptomatic, castrate-resistant, metastatic prostate cancer, with evidence of progressive disease, and a calculable PSA doubling time with at least 3 serum PSA values collected over a minimum of 3 months, will be invited to participate. These are subjects who would be eligible to receive sipuleucel-T as routine standard of clinical care. Subjects will be randomly assigned to a treatment group, stratified by pre-treatment estimated survival (< 18 months, ≥ 18 months), using the Halabi nomogram [50], and using laboratory/clinical data collected at screening for this determination. This stratification was chosen given the identification in a previous clinical trial that patients with more indolent disease characteristics appeared to have a greater benefit from vaccine treatment in terms of overall

survival, and the specific use of an 18-month cutoff is currently being used in prospective evaluation of other vaccine trials [51]. Given the absence of significant adverse events observed in previous clinical trials with either sipuleucel-T or pTVG-HP, no adverse events > grade 2 are anticipated. However, all study patients will be evaluated for evidence of toxicity, and further accrual to either treatment arm will be discontinued if the toxicity rate is deemed to be excessive. A toxicity rate of 20% for Grade 3 events (or Grade > 1 autoimmune events) or 10% Grade 4 events given an attribution of at least possibly related to study treatment will be considered excessive. Grade 3 limited site reactions (lasting < 48 hours) and fevers/chills (lasting < 48 hours) will be excluded from this assessment as expected possible adverse events of limited duration.

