3. Standard 1.5-2.0 peripheral blood cell leukapheresis – conducted at Dendreon-authorized center for sipuleucel-T collection.

H. Sipuleucel-T Infusion #3 – Day 32

1. Reinfusion of sipuleucel-T product – conducted at UWHC – standard-of-care protocol
2. Monitor patient for 30 minutes after completing infusion. Monitoring should include vital signs (including temperature, heart rate and blood pressure) and brief symptoms assessment by nursing staff prior to infusion and 30 minutes after infusion complete.

I. Sipuleucel-T Follow-Up Visit Day 43 (+/- 3 days)

1. Physical examination, symptoms assessment, and ECOG performance score
2. Blood draw for CBC with differential and platelets, chemistry panel, PSA and PAP
3. 10 ml peripheral blood (red-top tubes) for sera to evaluate antibody responses, and 100 ml peripheral blood (green-top heparinized tubes) for T-cell response evaluation and CTC analysis

ARM 2 SUBJECTS ONLY: DNA Immunization #1:

4. Subjects will receive pTVG-HP DNA immunizations intradermally on the deltoid area of the lateral arm (preferentially left arm) with 0.25 mL administered at each of two adjacent sites.
5. Following vaccinations, the subjects will be observed for 60 minutes for unanticipated adverse events and injection site inspection.

J. ARM 2 SUBJECTS ONLY: DNA Immunization #2 – Day 57 (+/- 3 days)

1. Immunization/GM-CSF and post-treatment monitoring as described above in section 9.I.4-5

K. ARM 2 SUBJECTS ONLY: DNA Immunization #3 – Day 71 (+/- 3 days)

1. Immunization/GM-CSF and post-treatment monitoring as described above in section 9.I.4-5

L. 3-Month Follow-up – Day 85 (+/- 7 days)

1. Physical examination, symptoms assessment, and ECOG performance score.
2. Blood draw for CBC with differential and platelets, chemistry panel, serum PSA and PAP
3. 10 ml peripheral blood (red-top tubes) for sera to evaluate antibody responses, and 100 ml peripheral blood (green-top heparinized tubes) for T-cell response evaluation and CTC analysis
4. CT scan of abdomen and pelvis, bone scintigraphy (can be performed +/- 7 days of this visit)

ARM 2 SUBJECTS ONLY: DNA Immunization #4:

5. Immunization/GM-CSF and post-treatment monitoring as described above in section 9.I.4-5

M. 6-month Follow-up – Week 24 (+/- 7 days)

1. Physical examination, symptoms assessment, and ECOG performance score
2. Blood draw for CBC with differential and platelets, chemistry panel, serum PSA and PAP (can occur up to 7 days prior to leukapheresis)

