3. CT scan of abdomen/pelvis and bone scintigraphy (can be performed +/- 7 days of this visit)
4. 10 ml peripheral blood (red-top tubes) for sera to evaluate antibody responses, and 20 ml peripheral blood (green-top heparinized tubes) for CTC analysis
5. Leukapheresis (~1.0 blood volume, 100 mL collection) for T-cell response evaluation (can be performed +/- 7 days of this study visit). If leukapheresis is not able to be obtained, then up to 150 ml of peripheral blood (green-top heparinized tubes) may be obtained via peripheral blood draw for the T-cell response evaluation.

ARM 2 SUBJECTS ONLY: DNA Immunization #5

6. Immunization/GM-CSF and post-treatment monitoring as described above in section 9.I.4-5

N. 9-Month Follow-up – Week 36 (+/- 7 days)

1. Physical examination, symptoms assessment, and ECOG performance score.
2. Blood draw for CBC with differential and platelets, chemistry panel, serum PSA and PAP
3. 10 ml peripheral blood (red-top tubes) for sera to evaluate antibody responses, and 100 ml peripheral blood (green-top heparinized tubes) for T-cell response evaluation and CTC analysis
4. CT scan of abdomen and pelvis, bone scintigraphy (can be performed +/- 7 days of this visit)

ARM 2 SUBJECTS ONLY: DNA Immunization #6

5. Immunization/GM-CSF and post-treatment monitoring as described above in section 9.I.4-5

O. OFF STUDY VISIT AND/OR 12-Month Follow-up – (week 48 +/- 7 days)

1. Physical examination, symptoms assessment, and ECOG performance score.
2. Blood draw for CBC with differential and platelets, chemistry panel, serum PSA and PAP
3. 10 ml peripheral blood (red-top tubes) for sera to evaluate antibody responses, and 100 ml peripheral blood (green-top heparinized tubes) for T-cell response evaluation and CTC analysis.
4. CT scan of abdomen and pelvis, bone scintigraphy (can be performed +/- 7 days of this visit, and does not need to be repeated for off-study visit if progression of disease already confirmed within 1 month)

P. Long-term Follow-Up

1. Subjects will be contacted by telephone (if not already being seen in clinic) annually (from registration) for up to 5 years to collect clinical information to identify any potential long-term risks. This information has been requested by FDA for all gene delivery trials to assess potential long-term risks. The specific information to be collected annually will include:
 - Date of contact
 - Current medications
 - Hospitalizations (dates and reasons for hospital admission)

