An adverse event is defined as any unfavorable and unintended sign (including abnormal laboratory finding unless they are grade 1 and deemed clinically insignificant), symptom or disease temporally associated with a medical treatment or procedure, regardless of whether it is considered related to the treatment or procedure. Note that for this study grade 1 laboratory values deemed clinically insignificant will not be reported as adverse events. Adverse events are categorized as definite, probable, possible, unlikely or unrelated in relation to the medical treatment or procedure performed. A life-threatening event is defined as any adverse event that places the subject, in the view of the investigator, at immediate risk of death from the reaction. All adverse events will be recorded from time of informed consent through 30 days after the final dose of study drug, as well as any time after these 30 days that the event is believed to be at least possibly related to study treatment. Serious adverse events are any events occurring that result in any of the following outcome:

1. Subject death
2. Life-threatening adverse event
3. In patient hospitalization or prolongation of existing hospitalization
4. Persistent or significant disability/incapacity
5. Congenital anomaly or birth defect

Adverse events are classified by organ system and graded by severity according to the current NIH Common Terminology Criteria, as described in Appendix A. The defined grades use the following general guidelines:

- 0 No adverse event or within normal limits
- 1 Mild adverse event
- 2 Moderate adverse event
- 3 Severe adverse event
- 4 Life-threatening or disabling adverse event
- 5 Fatal adverse event

B. Procedure for Reporting Adverse Events

Regulations defining the responsibilities for reporting adverse events are defined by the National Cancer Institute Cancer Therapy Evaluation Program (NCI CTEP, <http://ctep.info.nih.gov>). Please see the details of adverse event reporting in Section 14.C.

Appropriate clinical, diagnostic, and laboratory measures to attempt to delineate the cause of the adverse reaction in question must be performed and the results reported. All tests that reveal an abnormality considered to be drug- or treatment-related will be repeated at appropriate intervals until the course is determined or a return to normal values occurs. Information will be recorded as noted above.

12. Statistical Considerations

A. Overview

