consequences of the vaccination targeting other unrelated tissues. An intradermal route of administration will be used, and is preferred given the presence of Langerhans' antigen-presenting cells in the dermis. Intradermal administrations, however, carry a risk of immediate allergic reactions. For that reason, subjects will be monitored for 60 minutes following each treatment with evaluation of vital signs and examination of the skin site of treatment. Subjects will also be asked to keep a record of unusual site or other reactions for two days after immunization.

With respect to eliciting unwanted immunological reactions, PAP, a protein whose expression is essentially restricted to the prostate, does share homology with other tissue phosphatases, notably lysosomal acid phosphatase (LAP), most prevalent in pancreatic tissue. No such toxicity has been reported in clinical trials targeting PAP by means of a dendritic cell vaccine, and the generation of PAP-specific CTL in rat models similarly did not elicit detectable evidence of autoimmune disease in non-prostate tissues. Moreover, this was not seen in a previous phase I clinical trial with this DNA vaccine. However, in order to further evaluate this potential toxicity in humans, subjects will be evaluated at each visit by a review of systems based on the NCI common toxicity criteria. In addition, subjects will be examined and serum chemistries, including renal function tests, blood counts, liver function tests, and serum amylase, will be evaluated at 6-12 week intervals, as outlined above. The serum amylase will be used as a serum marker to monitor for evidence of subclinical pancreatic inflammation. While no autoimmune treatment-limiting adverse events have been observed to date, it is conceivable that by using a prime-boost strategy with different immunization approaches targeting the same PAP antigen could lead to more autoimmune events than either alone. For this reason, these blood tests will be continued to be monitored in this trial.

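### Adverse events of any attribution are recorded to about day 62 in Arm 1 but up to about day 283 in Arm 2, so a crude all-cause comparison by arm would tend to show more events in Arm 2

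*Combined protocol and SAP*

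**What the plan says.** **Recording rule.** Section 11.A sets the period for events of any attribution: "All adverse events will be recorded from time of informed consent through 30 days after the final dose of study drug". The sentence then keeps a narrower class open without a time limit: "as well as any time after these 30 days that the event is believed to be at least possibly related to study treatment". The term *study drug* is not defined for Arm 1, where sipuleucel-T is given as standard of care.

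**Last dose.** In Arm 1 it is the third infusion (Section 9: "H. Sipuleucel-T Infusion #3 – Day 32"). In Arm 2 it is the sixth DNA immunization ("ARM 2 SUBJECTS ONLY: DNA Immunization #6"), given at the visit headed "N. 9-Month Follow-up – Week 36 (+/- 7 days".

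**Assessments.** The Study Calendar row "Toxicity assessment ^b" applies to both arms at screening, days 15, 29, 43 and 85, and weeks 24, 36 and 48.

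**Safety question.** Section 15.A.1 says that priming and boosting against the same antigen "could lead to more autoimmune events than either alone".

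**Use of the data.** The stopping rule in Section 6.A counts at-least-possibly-related events within each arm. Section 14.A has toxicities discussed for each treatment arm, and Section 16.B sends the safety data to the study statistician. Section 12.G describes no analysis of adverse events.

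**The concern.** The visits are the same in both arms, but the recording rule follows the last dose, so it differs by arm. Four scheduled toxicity assessments (day 85 and weeks 24, 36 and 48) fall after all-cause recording has ended in Arm 1. Only week 48 falls after it has ended in a fully dosed Arm 2 patient.

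Between those two dates, the same event is entered in Arm 2 whatever its cause. In Arm 1 it is entered only if someone who knows the assignment attributes it to infusions that ended on day 32. Arm 1 is the only concurrent comparator for the autoimmune question in Section 15.A.1, and this weakens it over most of the booster period.

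**Working it through.** **Inputs.** The third infusion is on day 32 (Section 9.H) and immunization 6 is at week 36 (Section 9.N). Recording runs 30 days beyond the last dose (Section 11.A). Section 6 pairs weeks with days: "weeks 6 (day 43), 8 (day 57), 10 (day 71), 12 (month 3), then months 6 and 9". This gives day = 7 × week + 1, since 7 × 6 + 1 = 43, 7 × 8 + 1 = 57 and 7 × 10 + 1 = 71. The plan gives no figure of its own to reproduce.

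**End of all-cause recording.**
- Arm 1: 32 + 30 = day 62.
- Arm 2, all six immunizations: 7 × 36 + 1 = 253, and 253 + 30 = day 283 (276 to 290 with the ±7-day visit window).
- Difference: 283 − 62 = 221 days. A delay in the infusions moves both dates by the same amount.
- Arm 2, dosing stopped after immunization 4 (day 85): day 115. After immunization 5 (day 169): day 199.

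**Ratio of window lengths, fully dosed Arm 2 to Arm 1.**

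| Counted from | Arm 1 (days) | Arm 2 (days) | Ratio |
|---|---|---|---|
| Day 1 | 62 | 283 | 4.6 |
| Consent 28 days before day 1 (Section 9.A limit) | 90 | 311 | 3.5 |
| Consent 42 days before day 1 (Study Calendar limit, 4 + 2 weeks) | 104 | 325 | 3.1 |

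Counted from day 1, stopping after immunization 4 or 5 gives 115/62 = 1.9 or 199/62 = 3.2.

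**Effect on a crude table.** Assume the same constant rate of unrelated events in both arms. The documents give no such rate, so a range is shown. P(at least one) = 1 − exp(−rate × days / 365.25), counted from day 1 with full dosing.

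| Assumed rate per patient-year | Arm 1 (62 days) | Arm 2 (283 days) |
|---|---|---|
| 0.25 | 4% | 18% |
| 0.5 | 8% | 32% |
| 1 | 16% | 54% |
| 2 | 29% | 79% |

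At a rate of 1, an Arm 2 patient who stops after immunization 4 has 1 − exp(−115/365.25) = 27%, and after immunization 5 has 1 − exp(−199/365.25) = 42%. Counting from consent 42 days before day 1, the figures at that rate are 1 − exp(−104/365.25) = 25% in Arm 1 and 1 − exp(−325/365.25) = 59% in fully dosed Arm 2.

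**The case against.** A reader might infer that every safety table by arm is biased, or that Arm 1 cannot inform the autoimmune question at all. The documents do not support either reading.

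- Related events are recorded without a time limit in both arms, so a related-event table follows one formal rule. What remains there is attribution by unblinded investigators.
- The stopping rule uses related events within each arm, so day 62 does not cut it off.
- Section 12.G plans no adverse event comparison by arm, and safety is not a listed objective. No specified analysis is biased.
- Section 9.P provides annual contact for up to five years, for subjects in general. It asks about new autoimmune disorders and hospitalizations with no attribution filter. Chemistry, including amylase, continues in both arms to week 48.
- The late toxicity assessments do not contradict the recording rule, because they are needed to find related events.
- The 4.6 ratio is the upper end: it counts from day 1 and assumes full dosing. Patients leave study at radiographic progression after month 3, and some Arm 2 windows will be much shorter.

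All of this stands and limits the point. It does not remove it. Section 11.A is an explicit rule, and followed exactly it leaves unrelated-judged Arm 1 events unrecorded after about day 62. The items listed for annual contact do not include grading.

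The objection also holds that a change in the analysis alone would do. Cutting both arms at day 62 would keep only immunizations 1 and 2 (days 43 and 57) of six. Patient-time rates over unequal windows would set Arm 1's infusion weeks against Arm 2's infusion and booster months. That is a like-for-like comparison only if the rate is constant over time, and Section 15.A.6 describes infusion effects as typically lasting one to two days.

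**Conclusion.** The point holds for adverse events of any attribution. Recording in a fully dosed Arm 2 patient lasts about 221 days longer than in Arm 1, or 53 (115 − 62) or 137 (199 − 62) days longer if dosing stops after immunization 4 or 5. A crude all-cause summary by arm would tend to show more events in Arm 2 at equal true rates, and the concurrent control for the autoimmune question is weakened, though not lost.

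The conclusion does not extend to related-event tables under the written rule, to the stopping rule, or to new autoimmune disorders found at annual contact. It rests on three assumptions: that sipuleucel-T counts as study drug in Arm 1, that the rule is applied as written, and, for the percentages only, that the rates are equal and constant. It is a worthwhile correction to data collection and does not bear on the primary endpoint.

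**What to change.** In Section 11.A, record all adverse events in both arms from consent through the 12-month or off-study visit, using the toxicity assessments already in the calendar. Keep 30 days after the last dose as a minimum. State what counts as study drug in Arm 1.

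In Section 12.G, state that any all-cause adverse event summary by arm uses a common window or events per patient-time. This is still needed after the change in recording, because time on study may differ between arms when patients leave at progression.

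The cost is more adverse event entry, mainly in Arm 1. No visits are added.
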